7.6. Statistical analysis for Steady state (MAD part)

7.6.1. Endpoints/Variables

- Steady state will be assessed following repeat dose of GSK3494245 (MAD part) via analyses of trough plasma concentration (Ctau).

7.6.2. Main analytical approach

A statistical analysis will be performed using mixed effect model on log_e transformed endpoint.

- Fixed effect: log(dose)
- Random effect: Subject
- Data from all available doses will be considered. An unstructured covariance structure will be considered for the G matrix describing the between subject variability.
- The Kenward and Roger method for approximating the denominator degrees of freedom and correcting for bias in the estimated variance-covariance of the fixed effects will be used.
- Distributional assumptions underlying the model used for analysis will be examined by obtaining a normal probability plot of the residuals and a plot of the residuals versus the fitted values (i.e., checking the normality assumption and constant variance assumption of the model respectively) to gain confidence that the model assumptions are reasonable.
- If there are any departures from the distributional assumptions, alternative transformations such as data squared or square root of data, will be explored.
- If this model fails to converge, alternative covariance structures may be considered in the following order (1) Compound Symmetry (CS) and (2) Variance Components (VC) (3) First order autoregressive.

Model Results:

- The coefficients of the slopes for the day effect on log scale for each dose, along with corresponding 90% confidence intervals, will be used to determine whether steady state was achieved.

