	
Dose Proportionality (SAD part)
 
Dose proportionality will be assessed following single doses of GSK3494245 for fasted and fed cohorts separately(SAD part) via analyses of AUC(0-∞) and C_{max}.
 
A statistical analysis will be performed using the power model. The analysis will be performed on log_e-transformed data. For each of these parameters a mixed effects model will be fitted with log_e (dose) as a fixed effect and individual participant fitted as random effects. Estimates of the mean slopes of log_e (dose) will be reported along with corresponding 90% confidence intervals (slope\approx1 implies dose proportionality).
 
Accumulation (MAD part)
 
The extent of accumulation of GSK3494245 will be based on AUC (RAUC_(0-tau)), C_{max} (RC_{max}) and Ctau (RCtau).
 
The focus of the statistical analysis will be to estimate the accumulation ratio, Ro, on the pharmacokinetics of GSK3494245. Following log_e-transformation, AUC(0-tau) on Day 1 and AUC(0-tau) on the day of last dose will be analysed by a mixed effect model, fitting fixed effect terms for dose, day, and day by dose interaction, and fitting subject as a random effect.
 
For each dose, point estimates and 90% confidence intervals for the differences “Day 7 - Day 1” (for BID) or “Day 6 evening dose – Day 1 morning dose” (for TID) will be constructed using the appropriate error term. The point estimates and associated 90% confidence intervals will then be exponentially back-transformed to provide point and 90% confidence interval estimates for the ratios “Day 7: Day 1” (for BID) or “Day 6- Day 1” (for TID) for each active dose. If both the dose and day by dose interaction terms are not significant, a single point estimate and confidence interval pooled across all doses will also be constructed.
 
RC_{max} and RCtau will be estimated in a similar approach.
 
Steady State analysis (MAD part)
 
Steady state will be assessed following repeat dose of GSK3494245 (MAD part) via analyses of trough plasma concentration (Ctau)
 
A statistical analysis will be performed using mixed effect model on log_e transformed endpoint. A mixed effects model will be fitted with log_e (dose) as a fixed effect and subject fitted as random effect. The coefficients of the slopes for the day effect on log scale for each dose, along with corresponding 90% confidence intervals, will be used to determine whether steady state was achieved.

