 - a) Interest lies in the dose proportionality (i.e., slope) in the hypothetical situation where the treatment discontinuation had not occurred.
 - b) Interest lies in the overall treatment effect- The data post consumption of concomitant/prohibited medications (intercurrent event) will be analyzed as collected.

Secondary Estimands 3:

The clinical question of interest for the secondary objective is:

1. To examine dose accumulation following repeat doses of GSK3494245.
2. To examine time-invariance ratios of GSK3494245 following repeat doses
3. To assess steady state following repeat doses of GSK3494245

[figure not shown]
The estimand is described by the following attributes:

- **Population:** Healthy participants of age 18 to ≤ 55 years
- **Treatment condition:**
 - The MAD part will be a twice-daily (BID) or three times daily TID 7-day repeat dose design in up to 5 cohorts of participants (Cohorts 4, 5, 6, 7 and 8).
- **Endpoint:**
 1. AUC (RAUC_(0-tau)), RC_{max} and C_{tau} (RC_{tau})
 2. Ratio of AUC(0-tau) on day 7 to AUC (0- ∞) on day 1 or if TID is conducted, AUC(0-tau) on Day 6 evening dose to AUC (0- ∞) on Day 1
 3. C_{tau}
- **Population Level Summary measure:**
 1. For each dose, point estimates and 90% confidence intervals for the differences “Day 7 - Day 1” (for BID) or “Day 6 evening dose - Day 1 morning dose” (for TID) and the geometric mean ratio and 90% CI for the ratios “Day 7: Day 1”

(for BID) or “Day 6- Day 1” (for TID) after back transformation for each active dose.

2. Point estimate and 90% CIs of mean difference of ‘AUC(0-tau) at Day 7– AUC (0-∞) at Day 1’ based on the log-transformed data and after back-transformation of this estimated difference, the geometric mean of the ratio ‘AUC (0- tau) at Day 7: AUC (0-∞) at Day 1’ and 90 % CI of ratio for each active dose.
 3. Estimate of slope and corresponding 90% Confidence Interval CI for each active dose to assess steady state analysis.
- **Intercurrent events:**
 - a) Treatment discontinuation due to any reasons–Hypothetical strategy will be used.
 - b) Use of concomitant/prohibited medication – Treatment policy strategy will be used.
 - **Rationale for Estimand:**
 - a) Interest lies in the ratio between Day 7-Day 1 (for BID) or Day 6 – Day 1 (for TID) in the hypothetical situation where the treatment discontinuation had not occurred- The Day 1 data will be included even though Day 7 (for BID) or Day 6 (for TID) data is missing.

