7.5. Statistical analysis for Time Invariance (MAD part)

7.5.1. Endpoints/Variables

- The statistical analysis will be based on the ratio of AUC(0-tau) (i.e., AUC (0-12) for dosing is BID) on day 7 to AUC (0-∞) on day 1. If TID regimen is conducted, statistical analysis will be based on the ratio of AUC(0-tau) on Day 6 evening dose to AUC (0-∞) on Day 1.

Main analytical approach

A statistical analysis will be performed using mixed effect model on log_e transformed endpoint.

- Fixed effect: Day
 - Random effect: Subject
-
- Data from all available doses will be considered. An unstructured covariance structure will be considered for the G matrix describing the between subject variability.
 - The Kenward and Roger method for approximating the denominator degrees of freedom and correcting for bias in the estimated variance-covariance of the fixed effects will be used.
 - Distributional assumptions underlying the model used for analysis will be examined by obtaining a normal probability plot of the residuals and a plot of the residuals versus the fitted values (i.e., checking the normality assumption and constant variance assumption of the model respectively) to gain confidence that the model assumptions are reasonable.
 - If there are any departures from the distributional assumptions, alternative transformations such as data squared or square root of data, will be explored.

- If this model fails to converge, alternative covariance structures may be considered in the following order (1) Compound Symmetry (CS) and (2) Variance Components (VC) (3) First order autoregressive.

Model Results:

- The summary measure will be the point estimate and 90% CIs of mean difference of 'AUC(0-tau) at Day 7– AUC (0-∞) at Day 1' based on the log-transformed data and after back-transformation of this estimated difference, the geometric mean of the ratio 'AUC (0- tau) at Day 7: AUC(0-∞) at Day 1' and 90 % CI of ratio will also be presented for each active dose.

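### The steady-state model has no day term, although steady state is judged on day slopes per dose; the time-invariance model also leaves its per-dose ratios unspecified

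*SAP*

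**What the plan says.** **Steady state.** SAP 7.6.2 fits a mixed model to log-transformed Ctau. Its fixed-effect list holds log(dose) and nothing else, followed by "Random effect: Subject". Under the model results, "The coefficients of the slopes for the day effect on log scale for each dose, along with corresponding 90% confidence intervals" are to settle whether steady state was reached. The third secondary estimand in SAP 1.1.2 asks for the same kind of output: "Estimate of slope and corresponding 90% Confidence Interval CI for each active dose to assess steady state analysis". Protocol 9.5.2 enters log dose "as a fixed effect and subject fitted as random effect" and then also relies on "The coefficients of the slopes for the day effect on log scale for each dose".

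**Time invariance.** SAP 7.5 lists "Fixed effect: Day", with subject random and data from all doses used. The output is the geometric mean ratio of Day 7 AUC(0-tau) to Day 1 AUC(0-∞), and the "90 % CI of ratio will also be presented for each active dose". Protocol 9.5.2 defines this ratio but gives no model for it.

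**Accumulation, for comparison.** SAP 7.4.2 and protocol 9.5.2 use dose, day and their interaction, and report a ratio for each dose.

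**The concern.** Assessing steady state and time invariance are named secondary objectives of the MAD part (protocol section 3, SAP 1.1.1). In the steady-state section the quantity that decides the question is not a parameter of the model meant to supply it. A programmer following the text must add terms that nobody has prespecified: day as linear or categorical, one common slope or one per dose.

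For time invariance, the literal model averages over doses. If the ratio changes with dose, the average hides it. Protocol 4.5.1 gives a reason to look by dose: hepatocyte intrinsic clearance in dog and human was saturated at rising concentrations.

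**Working it through.** The point is one of model specification, so there is no stated power or sample-size figure to reproduce. The check is which quantities each written model can estimate.

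**Inputs.** Up to 5 MAD cohorts with 6 active participants each (SAP 1.2); morning troughs on Days 4 to 7 (SAP 1.1.1); AUC on Day 1 and Day 7 for BID dosing. Doses of 30, 60, 120, 180 and 240 mg come from protocol Table 6, which calls them illustrative. For simulation, between-subject SD 0.294 and within-subject SD 0.198 on the log scale are assumptions.

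**1. Steady state as written.** E[ln Ctau] = b0 + b1 × ln(dose), plus a subject effect: 2 fixed parameters. The expected difference between two days at the same dose is identically 0 at all five doses because day does not appear. The model gives 0 of the 5 required slopes.

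**2. Can another reading rescue it?** Fitted within one dose, ln(dose) is constant and collinear with the intercept (rank 1 of 2), and there is still no day term. The unstructured G matrix does not help either. The only random effect named is subject, and a random day slope without a fixed day effect would have mean zero by construction.

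**3. Steady state with dose (factor), day (continuous) and dose*day.** There are 5 intercepts + 5 slopes = 10 fixed parameters, and 5 × 6 × 4 = 120 troughs. All five day slopes are estimable. One simulated data set, which shows estimability and not performance, gave:

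| Dose (mg) | True slope per day | Estimate | 90% CI |
|---|---|---|---|
| 30 | 0 | -0.02 | -0.08 to 0.03 |
| 60 | 0 | -0.01 | -0.07 to 0.05 |
| 120 | 0.05 | 0.10 | 0.05 to 0.16 |
| 180 | 0.15 | 0.21 | 0.15 to 0.27 |
| 240 | 0.25 | 0.25 | 0.20 to 0.31 |

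The written model, fitted to the same data, returned an intercept and a log-dose slope of 1.05 (simulated as 1) and nothing about days.

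**4. Time invariance as written.** E[ln AUC] = c0 + c1 × day, plus a subject effect: 2 fixed parameters and one ratio, exp(c1). With simulated true ratios of 1.0, 1.0, 1.1, 1.3 and 1.6, it returned the single value 1.26.

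**5. Time invariance with dose, day and dose*day.** There are 10 fixed parameters and 5 × 6 × 2 = 60 AUC values. All five ratios are estimable: 1.11, 1.00, 1.26, 1.22 and 1.85 on the same data. Their geometric mean is 1.26, which is the pooled value in step 4.

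**6. Time invariance, day-only model fitted within each dose.** On these balanced data the point estimates are the same five ratios as in step 5.

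**The case against.** The best defence concerns time invariance. A promise of a ratio for each dose can be read as a day-only model run within each dose, and step 6 shows that this delivers the ratios. The sentence about using data from all doses recurs across SAP section 7 and may mean only that no dose is left out. This stands: SAP 7.5 is ambiguous, not unworkable. A reader who infers that neither model can produce its result goes too far.

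For steady state, a reader might infer that the trial would report a dose-proportionality slope near 1 in place of a time trend. The documents do not support that. They name the output as a day slope per dose, which a single log(dose) slope cannot supply, so the gap should surface at programming. They also predict no dose slope for Ctau. The nearest figure is mean AUC0-24 in protocol Table 6, which rises from 1819 to 16955 over an 8-fold dose range: ln(9.32)/ln(8) = 1.07. That also suggests only mild non-linearity, so a large dose-dependent signal being lost is possible but not shown. Nor is the steady-state information lost: the troughs are still collected and listed.

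A reader might also expect that omitting dose from SAP 7.5 inflates the interval by pushing the dose range into subject variance. In complete Day 1/Day 7 pairs, dose cancels from the within-subject contrast. It could matter somewhat where Day 7 is missing, because SAP 1.1.2 keeps those Day 1 records; the size is not established.

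Finally, the stakes are limited. Protocol 9.5.2 words both assessments as optional. Escalation rests on exposure thresholds and a separate power model (protocol 7.1.1). With a half-life of about 4 h (protocol 4.4), Day 4 morning is 72/4 = 18 half-lives after the first dose, so a wrong conclusion on steady state is unlikely. This lowers the severity but does not supply the missing term.

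**Conclusion.** The steady-state mismatch is confirmed in both SAP 7.6.2 and protocol 9.5.2. The stated decision quantity cannot be estimated from the stated model under pooled or by-dose fitting: 0 of up to 5 slopes. This follows from the model terms alone and does not depend on the illustrative doses or the simulation values.

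The time-invariance point is secondary. Taken literally, SAP 7.5 gives 1 pooled ratio instead of up to 5; with an unstated by-dose fit it gives all of them.

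Both analyses are secondary and estimation-only, with no hypothesis tested. Alpha, power, sample size, dose escalation and the primary safety analysis are untouched. This is a correction that should be made, not one on which the trial's main conclusions depend.

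**What to change.** - **SAP 7.6.2 and protocol 9.5.2 (steady state):** model loge(Ctau) on Days 4 to 7 with dose (factor), day (continuous) and dose*day as fixed effects and subject as random effect. Report the day slope with its 90% CI for each dose, judged against 0.
- **SAP 7.5 (time invariance):** use dose, day and dose*day as in SAP 7.4.2 and report the within-dose contrast. Alternatively, state that the day model is fitted separately by dose.
- **Both:** analyse BID and TID cohorts separately if both occur. The dosing interval differs (12 h and 6 h), and so does the time-invariance comparison occasion (Day 7 and the Day 6 evening dose).

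The cost is a few lines of text. No extra samples or participants are needed. The change is best made before database release, which is when protocol 9.5 requires the analysis plan to be final.

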7.6.2.1. Intercurrent events and handling of missing data

The intercurrent events mentioned in Section 1.1.2. along with the corresponding strategies will be considered during this analysis.

- For treatment discontinuation due to any reason:

Subjects' data available up to the withdrawal will be included in the analysis where treatment discontinuation had not occurred. If a subject withdraws consent during a period, the missing data post withdrawal will not be imputed.

- For Subject use concomitant/prohibited medication:

The subject data post consumption of concomitant/prohibited medications (intercurrent event) will be analyzed as collected.

If multiple intercurrent events are observed, then the data will be handled using more than one strategy as described in Section 1.1.2. and interpretations of the results will be made accordingly.

Graphical presentations will be provided, if appropriate. All data will be listed. Details of the planned displays are provided in the Output Programming Specification (OPS) document. Data Displays will be based on GSK Data Standards and statistical principles.

7.7. Other Analysis

Dose proportionality will be assessed following multiple doses of GSK3494245 for the Multiple Ascending Dose (MAD) via analyses of AUC (0- ∞) and C_{max} for Day 7 (BID) or Day 6 (TID) and Day 1. Please refer Section 7.3.2 Main analytical approach for the statistical analysis procedure.

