1.1. Objectives, Estimands and Endpoints

1.1.1. Objectives and Endpoints

Objectives	Endpoints
Primary Objectives	Primary Endpoints

 To evaluate the safety and tolerability of single and repeat doses of GSK3494245 in healthy participants. 	Adverse event reporting, treatment emergent, clinically significant changes from baseline in clinical laboratory, safety data, physical examinations*, vital signs, 12 lead electrocardiograms (ECGs) and telemetry.
Secondary Objectives	Secondary Endpoints

 To evaluate the PK profile of single (fasted and fed) and repeat doses of GSK3494245 in healthy participants. 	
 SAD Part: Derived PK parameters for GSK3494245 following single dose (fasted and fed) including area under the plasma drug concentration versus time curve (AUC(0-t), AUC (0-∞), maximum observed plasma drug concentration (C_{max}), time to maximum observed plasma drug concentration (T_{max}), and apparent terminal half-life (t_{1/2}) as data allow. MAD part: as appropriate: 
 Day 1 AUC(0-t), AUC (0-∞), AUC(0-tau), C_{max}, T_{max}, t_{1/2} Day 4-7 morning trough plasma concentration (C_{tau}) Day 7 AUC(0-t), AUC(0-tau), C_{max}, T_{max}, t_{1/2}, CL_{ss} Additionally, for TID regimen if conducted): Day 6 evening dose AUC (0-t), AUC(0-tau), C_{max}, T_{max},

Objectives	Endpoints

 To examine dose proportionality following single doses of GSK3494245 To assess accumulation and time-invariance ratios of GSK3494245 To assess steady state following repeat doses of GSK3494245 	
 Dose-proportionality assessment using derived PK parameters AUC, Cmax, as data allows. SAD part: AUC (0-∞), Cmax MAD part: 
 Accumulation ratios assessment*, where data allow: RAUC(0-tau), RCmax, RCtau. Time-invariance ratio calculation as AUC (0-tau on Day 7 to AUC (0-∞) on Day 1. Additionally, for TID regimen if conducted: Time-invariance ratio calculation for TID regimen as AUC(0-tau) on Day 6 evening dose to AUC (0-∞) on Day 1 Steady state assessment for MAD part: Ctau

CCI

* Physical examination is not captured in the study CRF but documented only at the site. However, all clinically significant findings on physical examination will be reported as adverse events.

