7.3.2. Main analytical approach

Power model will also be fitted to assess dose proportionality as follows: $y = \alpha * \text{dose}^\beta$. In the log transformed manner this power model can be written as following

$$\log_e(Y) = \beta \times \log_e(\text{dose}) + \log_e(\alpha)$$

Where, y denotes the PK parameter being analyzed, dose denotes the dose administered to a subject. α depends upon random intercept subject effect and period effect and β is the coefficient of covariate $\log(\text{dose})$.

Log_e transformed data will be analyzed using a mixed effect model:

- Fixed effect: loge (dose), period
 - Random effect: Subject
- Data from all available doses will be considered. An unstructured covariance structure will be considered for the G matrix describing the between subject variability. If this model fails to converge, alternative covariance structures may be considered such as Variance Component, Compound Symmetry, etc. Akaike's Information Criteria (AIC) will be used to assist with the selection of covariance structure.
 - The Kenward and Roger method for approximating the denominator degrees of freedom and correcting for bias in the estimated variance-covariance of the fixed effects will be used.
 - Distributional assumptions underlying the model used for analysis will be examined by obtaining a normal probability plot of the residuals and a plot of the residuals versus the fitted values (i.e., checking the normality assumption and constant variance assumption of the model respectively) to gain confidence that the model assumptions are reasonable.
 - If there are any departures from the distributional assumptions, alternative transformations, such as data squared or square root of data, will be explored.

Model Results:

- The estimates mean slopes and 90% CIs of $\log_e(\text{dose})$ will be presented. Note that a slope ≈ 1 implies dose proportionality.

If the power model is failed to converge, analysis will be performed using Analysis of Variance (ANOVA) model to assess dose proportionality. The PK parameters (AUC (0- ∞), Cmax) will be dose-normalized first and multiplying by reference dose prior to loge-transformation, will be analyzed separately using mixed effects model.

- Fixed effect: loge (dose), period
- Random effect: Subject

The reference dose will be chosen based on the lowest clinically relevant dose over which PK can be adequately described.

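### SAP 7.7 bases multiple-dose dose proportionality on AUC(0-∞) on Day 7 or Day 6, where the plan does not list that parameter, and borrows the crossover model of 7.3.2 unchanged

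*SAP*

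**What the plan says.** SAP 7.7 (Other Analysis) adds an analysis of the MAD part: "Dose proportionality will be assessed following multiple doses of GSK3494245 for the Multiple Ascending Dose (MAD) via analyses of AUC (0". The parameter cut off at the end of that quote is AUC(0-∞), and the second parameter is Cmax. The days are given as "for Day 7 (BID) or Day 6 (TID) and Day 1". For the method, the section says only "Please refer Section 7.3.2 Main analytical approach for the statistical analysis procedure".

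The MAD parameter lists (SAP 1.1.1 and 1.1.2; Protocol 1.1 and 3) include AUC(0-∞) for Day 1. For the last dosing day they give "Day 7 AUC(0-t), AUC(0-tau), C_{max}, T_{max}, t_{1/2}, CL_{ss", and for TID they add "Day 6 evening dose AUC (0-t), AUC(0-tau" along with Cmax and Tmax. Neither of these later lists contains AUC(0-∞), and the Day 6 list has no half-life either.

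SAP 7.3.2 is written for the single-dose crossover cohorts. Its terms are "Fixed effect: loge (dose), period" with participant random, and its intercept "depends upon random intercept subject effect and period effect". The ANOVA fallback repeats the period and participant terms.

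The MAD part is parallel-group, with one intervention period per cohort (Protocol 1.1), and a participant may join only one cohort (Protocol 4.1). For TID, the profile after the Day 6 evening dose is sampled to 6 h (Protocol 1.3.2). SAP Table 1 flags AUC(0-∞) when more than 20% is extrapolated and excludes it from summary statistics above 30%.

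**The concern.** There are two separate problems.

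**Parameter.** AUC(0-∞) counted from a late dose is the area from that dose plus whatever remains of all earlier doses. It is neither a single-dose exposure nor the exposure over a dosing interval. Under linear kinetics this does no harm to the slope, because every AUC scales with dose. If clearance saturates, the leftover area grows faster than dose, and an AUC(0-∞) slope overstates the departure from proportionality. Saturation is a live question here: Protocol 4.5.1 reports that intrinsic clearance in human hepatocytes saturates with rising concentration, and Protocol Table 6 predicts slightly more than proportional AUC. For TID the parameter also leans on extrapolation from a 6 h profile.

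**Model.** Each MAD participant has one dose level, one period and one value per day. Section 7.3.2 was built for several doses and periods per participant. Section 7.7 does not say which terms to drop, or whether Day 1 and Day 7/6 are fitted separately or together. The programmer would have to decide, possibly after seeing the data.

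**Working it through.** **Plan's own figures.** The only design figure stated for the MAD cohorts is 36% precision with 6 participants and CVb 30% (SAP 8). SD = √ln(1 + 0.30²) = 0.294; half-width = 2.571 × 0.294/√6 = 0.308; exp(0.308) − 1 = 36%. It reproduces. The half-life of about 4 h (Protocol 4.4) agrees with the low-clearance scenario: ln 2 × 1.28/(3.81 × 0.06) = 3.88 h.

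**Model terms.** Take 5 doses × 6 active participants, one value each.
- Period is constant, so it repeats the intercept: rank 2 of 3 columns. Read as cohort instead, it is aliased with loge(dose): rank 5 of 6.
- With one value per participant, the likelihood depends only on the sum of participant and residual variance. For a simulated data set it is 0.478724 whether the participant share is 0, 0.3, 0.6 or 0.9.
- With loge(dose) alone the slope is estimable. For the illustrative Table 6 doses (30, 60, 120, 180, 240 mg), Sxx = 17.13 on 28 df, and the 90% CI half-width is 1.701 × 0.294/√17.13 = 0.12 at CVb 30% (0.08 at 20%, 0.16 at 40%).

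**Size of the carry-over.** One-compartment superposition with Protocol Table 3 values: V 1.28 L/kg, KA 0.7 per h, CL 3.81 or 6.67 mL/min/kg, so k = 0.1786 or 0.3127 per h. The share of a single dose's AUC(0-∞) lying beyond time t is

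T(t) = [KA·exp(−kt) − k·exp(−KA·t)]/(KA − k).

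AUC(0-∞) counted from the last dose, in single-dose units, is the sum of T over the ages of all doses given. The area beyond w hours is the same sum with w added to each age.

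*Low clearance.* T(6) = 0.455, T(12) = 0.157, T(18) = 0.054, T(24) = 0.018, T(30) = 0.006, T(36) = 0.002.
- BID Day 7 (ages 0, 12, 24, 36, …): 1 + 0.157 + 0.018 + 0.002 + … = 1.178. AUC(0-12) = 1.000.
- TID Day 6 evening (ages 0, 6, 12, 24, 30, 36, …): 1 + 0.455 + 0.157 + 0.018 + 0.006 + 0.002 + … = 1.639. Beyond 6 h: 0.455 + 0.157 + 0.054 + 0.006 + 0.002 + … = 0.675. AUC(0-6) = 1.639 − 0.675 = 0.964; ratio 1.70; extrapolated share 0.675/1.639 = 41%.

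*High clearance.* BID ratio 1.043. TID AUC(0-∞) = 1.308, AUC(0-6) = 0.994, ratio 1.32, extrapolated share 24%.

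**Shorter half-life.** Table 6 is based on SAD data up to 160 mg. Its mean Cmax divided by half its mean AUC(0-24) is 464.1/909.5 = 0.51 per h at 30 mg and 2978/8477.5 = 0.35 per h at 240 mg. In a one-compartment model this ratio is roughly a lower bound on the elimination rate, so the half-life is at most about ln 2/0.51 = 1.4 h and ln 2/0.35 = 2.0 h. I take 1.4–2.0 h as an assumption.

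| Half-life, KA | BID Day 7 excess | TID Day 6 evening excess | TID extrapolated |
|---|---|---|---|
| 2.0 h, 0.7 per h | 3.1% | 27% | 21% |
| 1.4 h, 0.7 per h | 0.8% | 15% | 13% |
| 1.4 h, 1.3 per h (assumed) | 0.4% | 9% | 8% |

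Faster absorption lowers the TID figures further: at 1.4 h and KA 4 per h, the excess and the extrapolated share are each about 6%.

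**Effect on the slope.** Linear kinetics give a slope of 1 with either parameter. As an illustration only, I replaced linear clearance in the high-clearance scenario (70 kg) with saturable clearance, Km assumed at 1–6 mg/L, over 30–240 mg. BID slopes on AUC(0-tau) and AUC(0-∞) were 1.28 and 1.30 at Km 1, and 1.04 and 1.05 at Km 6. TID slopes were 1.45 and 1.64 at Km 1, and 1.07 and 1.08 at Km 6. For scale, Table 6 predicts a 9.3-fold AUC (16955/1819) over an 8-fold dose range, a slope of ln 9.32/ln 8 = 1.07.

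**The case against.** The strongest reply is that this is a slip in a supplementary analysis. The protocol and the SAP objectives confine dose proportionality to single doses. Section 7.7 sits under other analyses, nothing is tested (SAP 2), and in-study escalation has its own exposure model (Protocol 7.1.1). That stands, and it limits the importance.

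The parameter mismatch is also narrow. Cmax is listed on every day and AUC(0-∞) on Day 1. Day 7 lists a half-life and is sampled to 14 h, and SAP Table 1 does not tie AUC(0-∞) to a day, so a Day 7 value could be computed. That stands too. What remains is that the computed value would still contain earlier doses.

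The large extrapolation figures come from pre-study predictions. Table 6 points to faster kinetics, under which the TID share may not reach the 20% flag. This is a fair correction to the size. It does not settle the matter: the half-life bound assumes one compartment and uses ratios of means, MAD dosing is fed, and Protocol 4.4 still gives about 4 h. For TID, the Day 7 pre-dose sample could extend the evening profile and reduce extrapolation, but 7.7 does not provide for that and the carry-over would stay.

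A reader might infer that the analysis cannot be run, or that the power model has no use in parallel groups. The documents do not support that: the redundant period column leaves the slope unchanged, and the unidentified variance split leaves the likelihood unchanged. A reader might also infer that single-dose and steady-state slopes will be averaged. That follows only if the days are stacked, and 7.7 can equally be read as by-day.

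**Conclusion.** The point holds as a specification error. Section 7.7 names, for Day 7 or Day 6, an AUC that the parameter lists do not give there and that is not the steady-state exposure. It also imports a model with one redundant term, one variance that cannot be identified when a single day is analysed, and no day term if days are pooled.

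The excess of AUC(0-∞) over AUC(0-tau) is small for BID: 4–18% with Table 3 values, about 0–3% with half-lives of 1.4–2.0 h. For TID it is larger: 32–70% with 24–41% extrapolated, or about 9–27% with 8–21% extrapolated. The Table 3 figures are the high end. All rest on one-compartment linear superposition, and the lower range also rests on the assumed half-lives and absorption rates.

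The excess biases the slope only if kinetics are non-linear. In the illustration the bias exceeds the 0.12 half-width only for TID under the strongest saturation tried (1.64 against 1.45). It would be wrong to conclude that the planned slope is generally misleading, or that dose choice for later studies depends on 7.7; no passage says so.

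**What to change.** Rewrite SAP 7.7 as one self-contained paragraph:
- **Parameters.** AUC(0-tau) and Cmax for Day 7 (BID) or the Day 6 evening dose (TID). AUC(0-tau) and Cmax for Day 1, with Day 1 AUC(0-∞) as data permit.
- **Model.** Replace the reference to 7.3.2 with a power model having loge(dose) as the only fixed effect, fitted separately by day, with no period term and no separate participant variance. If days are to be pooled, use loge(dose), day and their interaction as fixed effects with participant random; SAP 7.4.2 already has a similar structure.
- **Regimens and output.** Fit BID and TID cohorts separately and report the slope with its 90% CI for each day.
- **Status.** State that the analysis is additional to the protocol, which limits dose proportionality to the SAD part.

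The cost is one SAP paragraph, agreed before database release. The parameters are already in the plan's lists, so no new sampling is needed.
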